## 6.2 Other Baseline characteristics

The prior Ig treatments taken four months before the Randomization visit will be listed and summarized for the RS by treatment group and for all participants. Listing will include the reported term, preferred term, dose, route of administration, frequency, formulation, start/stop dates and duration (in days). For definition of prior treatments see Section 6.4.1.

Duration will be calculated as follows:

$$\text{Duration (in days)} = ((\text{End date of Ig treatment date} - \text{Start date of Ig treatment}) + 1)$$

In addition, the following variables will be listed and summarized at baseline for the RS by treatment group:

- iRODS score (raw sum score, logit locations and centile metric scores)
- INCAT
- Grip strength (assessed by site personnel and patient reported grip strength)
- Immunological variables (IgG [including total IgG and IgG subclasses], IgM, IgA, IgE)
- Cytokines
- Serum (C3 and C4) and plasma complement levels (C3a and C5a)
- Duration of disease (years)

Duration of disease (years) will be calculated as:

$$\text{Duration of disease} = \frac{\text{Date of randomization} - \text{Date of initial CIDP diagnosis} + 1}{365.25}$$

If the date of initial CIDP diagnosis is partial, it should be imputed to the most recent feasible date (ie, last day of the month if only day is missing, or the last day of the year if day and month are missing). Note that if the date of randomization is missing then the duration of disease will be derived using the date of screening.

### **6.3 Medical and procedures history**

Past medications will include any medications that started and stopped before the first administration of IMP. Medical history will be listed and summarized for the RS by treatment group and will include the MedDRA system organ class (SOC), high level term (HLT) and preferred term (PT). Procedure history and concomitant medical procedures will be listed based on the RS.

History of CIDP will be listed for RS.

### **6.4 Prior and concomitant medications**

Prior and concomitant medications will be listed and summarized for the RS by treatment group and for all participants and will include the WHODD Anatomical Main Group [Level 1], Therapeutic Subgroup [Level 2], PT and reported term. The listing will also include the dose per intake and unit, frequency, formulation, route of administration, indication, category (prior and concomitant, prior, or concomitant) and both start and end date (or ongoing, if applicable).

- Prior medications will include any medications that started before the first administration of IMP.
- Prior and concomitant medications will include any medications that started prior to dosing and continued after.
- Concomitant medications will include any medications that have been taken at least once after the first administration of IMP during the Treatment and/or Observation Period.

#### **6.4.1 Prior medication definition**

Prior medications will include any medications that started prior to the first administration of IMP. This includes any medications that started and stopped prior to dosing as well as those

which started prior to dosing and continued after (classified as prior and concomitant medications).

#### 6.4.2 Concomitant medication definition

Concomitant medications will include any medication that has been taken at least once (on or after the first administration of IMP) during the Dosing Period and/or the Observation Period.

Any medication that started prior to the first administration of IMP and continued after dosing will be classified as prior and concomitant. Any medication that started on or after the first administration of IMP will be classified as concomitant only.

Any medications with missing dates and/or times will be handled as described in Section 4.2.7 in order to classify them as prior or concomitant.

The following rules will be used to assign concomitant medications to the study periods:

- Treatment Period: a medication will be assigned to Treatment Period if it has been taken at least once between the first administration of IMP until Visit 17/PEOT (non inclusively). This includes medications that started prior to the first IMP and continued during Treatment Period and those that continued into the Observation Period.
- Observation Period: a medication will be assigned to Observation Period if it has been taken at least once between day 85 (Visit 17/PEOT) and the Final visit or end of study participation. This includes medications that started prior to the Observation Period.

Medications taken during both study period will be listed once, but the study period will indicate both study periods.

## 7 MEASUREMENTS OF TREATMENT COMPLIANCE

The study medication will be administered and monitored by the investigator or designee. Any dosing deviations (eg, incomplete infusion volume administered, infusion temporarily interrupted, infusion discontinued) will be discussed at the DEM and any actions taken regarding the analyses will be documented accordingly and discussed in the CSR.

All drug administration details (including exposure category described in Section 10.1, date, start and stop time of infusion, interruptions, discontinuations, total planned volume and actual volume delivered, planned and actual infusion rates, location of infusion site) will be listed. The reasons for any interruptions or discontinuations will be included in the listing. The duration of the infusion, in minutes, and compliance will also be calculated and presented.

Compliance, percent of planned dose administered, will be calculated based on the planned and actual volume delivered as follows:

Percent of Planned dose administered = (Total actual volume delivered (mL)/Total planned volume (mL))\*100

Actual volume delivered and total planned volume (i.e. according to section 7.2 of protocol) will be captured in the eCRF. In case of interruption the sum of actual volumes delivered, and the total planned volume recorded into the eCRF will be used for the calculation.

There will be no specific analysis of compliance.

## 8 EFFICACY ANALYSES

All analyses of the efficacy variables will be performed on the FAS. Additional outputs may be repeated for the PPS or the MFAS where indicated. Listings will be based on the SS.

Treatment group assignment for efficacy analysis will be according to the actual treatment regimen.

All efficacy analyses are to be interpreted as exploratory analyses. No p-values will be presented.

Any efficacy measurements are considered invalid, if the participant received rescue medication before the assessment. Assessments collected at the same day as first intake of rescue medication are considered valid. Respective measurements will not be used for summary tables and MMRM, but kept in listings. This includes iRODS, INCAT, clinician reported grip strength, RT-MRC, CIDP PRO and Fatigue, PGIS, PGIC and the patient reported grip strength as derived in Section 8.2.4.

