### **7.7.3      Rescue medication**

If, at any time during the Treatment and Observation Period, the subject relapses according to the predefined criteria for relapse as specified in Section [4.1.2](#) using the subject's score on iRODS, INCAT, or maximum grip strength (assessed by site personnel), and supported by the medical judgement of the investigator, then rescue medication must be considered and the subject will be withdrawn from IMP (see Section [6.4](#)). The subject will return to the SOC Ig treatment (eg, IVIg of 2g/kg) as rescue medication at the time of relapse at the discretion of the investigator. The subject will have the opportunity to be stabilized over a period of 2 weeks to maximum 12 weeks starting from the relapse visit (ie, PEOT or later visit; see Section [8.3](#)). Once stabilized, the subject who completed the Treatment Period with no CIDP relapse, will be offered the possibility to enter in the OLE (CIDP04) and be treated with rozanolixizumab from that moment onward. The subject will complete the FV (V21) and enter the OLE on the same day. If a subject relapses during Treatment Period or does not wish to enter the OLE, the subject will continue their SOC treatment after stabilization. They will continue the stabilization visit schedule (every 1 to 3 weeks) until they have a follow-up of 12 weeks after last IMP dose.

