**Table 8–1: Management of Observation and Stabilization Periods**

Subject status	Stabilization with rescue medication?	Ability to enter OLE?	End of study CIDP01
Subject completes Treatment Period without CIDP relapse (all visits performed until Visit 17)	NA	yes	

• Last Visit=Visit 17=Entry visit in OLE (CIDP04)

	NA	no	
If the subject wants to return immediately to SOC:
 

• Subject returns to treatment with SOC (eg, IVIG or SCIG) during Observation Period.

• Time of required follow-up since last IMP dose is 12 weeks.

• Subject attends Visit 17 to Visit 21 (FV=last visit).

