**Table 8–1: Management of Observation and Stabilization Periods**

Subject status	Stabilization with rescue medication?	Ability to enter OLE?	End of study CIDP01
** CIDP relapse during Observation Period (after Visit 17) for subjects who completed Treatment Period	yes	yes	

Subject starts stabilization for minimum of 2 weeks and maximum 12 weeks with rescue medication. Visits are scheduled every 1 to 3 weeks.

If relapse happens towards the end of the 12-week Observation Period, overall timeframe (ie, since PEOT, including IMP free and stabilization period) until entry in OLE can be up to 24 weeks from last IMP dose.

FV (V21)=Last visit after stabilization visits=Entry visit in OLE (CIDP04).

	yes	no	

Subject starts stabilization for a minimum of 2 weeks and a maximum of 12 weeks with rescue medication. Visits are scheduled every 1 to 3 weeks.

Subject continues SOC after stabilization. Time of required follow-up since last IMP dose is 12 weeks. Stabilization visit schedule still applies (every 1 to 3 weeks).

FV (V21)=Last visit after stabilization visits.

Withdrawal for other reasons than CIDP relapse (before Visit 17)	no	no	

Subject attends PEOT Visit

IMP is stopped

Subject returns to treatment with SOC (eg, IVIg or SCIG) during Observation Period

Time of required follow-up since last IMP dose is 12 weeks

Subject attends Visit 17 to Visit 21 (FV=Final Visit)

CIDP=chronic inflammatory demyelinating polyradiculoneuropathy; FV=Final Visit; ICF=informed consent form; IMP=investigational medicinal product; IVIg=intravenous immunoglobulin; OLE=Open-Label Extension; PEOT=premature end of treatment; SCIG=subcutaneous immunoglobulin; SOC=standard of care

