#### **3.5.4 Full Analysis Set**

The Full Analysis Set (FAS) will consist of all participants in the SS, who have a Baseline and at least one valid post-Baseline iRODS measurement up to Visit 17/PEOT (inclusively).

Measurements are considered invalid if the participant received rescue medication before the assessment of iRODS. Assessments collected at the same day as first intake of rescue medication are considered valid. Invalid measurements will not be used for summary tables and MMRM, but kept in listings.

The FAS is the primary analysis set for efficacy analyses. In the case of mistreatment, participants will be analyzed as treated if the participant received the incorrect treatment for the entire study period. In the case of partial mistreatment, patients should be analyzed as randomized, but considered as protocol violators. As for the SS, in the case of mistreatment participants will be primarily analyzed as treated. However, if applicable, sensitivity analyses will also be performed according to the randomized treatment group.

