### **3.9 Changes to protocol-defined analyses**

- The definition of the SS has been updated to include all subjects who received at least one dose of the IMP.
- FAS definition:
  - Study participants will be analysed as actually treated only if they received the incorrect treatment for the entire study period. In case of partial mistreatment, the participant will be analyzed as randomized.
  - The FAS definition is clarified being limited to valid primary efficacy results up to V17 only as the primary efficacy endpoint is the change in iRODS from baseline to V17.
- To prevent bias in efficacy evaluation, an efficacy assessment is considered invalid, if that assessment follows the first intake of rescue medication. Assessments on the same day as first intake of rescue medication are valid.
- The protocol specifies the primary efficacy analysis covariate “prior Ig therapy” in section 14.3.1. Prior Ig therapy is defined by the stratification factor route of administration of prior Ig therapy.
- The MFAS was included as an additional analysis set in the SAP and was not part of the final clinical study protocol (CSP). This was added as the sensitivity analysis, to ensure the robustness of the efficacy analysis results in relation to dose variation, as foreseen in the CSP.
- Hy’s Law, defined in the protocol as

**$\geq 3 \times \text{ULN}$  ALT or AST with coexisting  $\geq 2 \times \text{ULN}$  total bilirubin in the absence of  $\geq 2 \times \text{ULN}$  ALP**

will instead be defined as

**(ALT or AST increase  $> 3 \times \text{ULN}$ ) and Total bilirubin  $> 2 \times \text{ULN}$  and ALP  $< 2 \times \text{ULN}$**   
to match program standards and general medical definitions.

- The study variable “Change in CIDP-specific auto-antibody levels in serum from Baseline during Treatment and Observation Periods” will not be analyzed in scope of this SAP. Sampling dates are captured in the CRF and will be listed. The samples’ results will not be part of this study’s database and instead analyzed and reported separately. The same is true for exploratory biomarkers RNA, proteins and metabolites variables.

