### **4.2 Handling of dropouts or missing data**

#### **4.2.1 Efficacy data**

For participants who prematurely withdraw for any reason before Week 13 (Day 85), data collected during the PEOT Visit will be used to impute iRODS, INCAT and grip strength at the closest missing visit. In case a participant discontinues the study prematurely, the assessment of the PEOT visit will be mapped to closest missing visit according to the visit schedule utilizing the relative day in study to a maximum of day 85 (Visit 17). However, if a participant receives rescue medication prior to the PEOT visit, the assessment will be regarded invalid and only listed. Assessments on the same day as first intake of rescue medication is acceptable for analysis.

Since the analysis is based on the mixed model repeated measures (MMRM) approach, visits beyond the PEOT Visit will not be imputed. Missing data in-between visits will be covered by the MMRM approach.

For additional analyses of iRODS score to account for missing data, last observation carried forward (LOCF) and multiple imputation will be applied to address the issue of missing scores (see Section 8.1.3). There will be no imputation of missing individual item scores in the summaries for the iRODS; only to the overall iRODS score.

For the analysis of relapse data, participants who withdraw from the study for any reason before Week 13 (Day 85) or who have missing data at Week 13 (Day 85) will be considered as relapsed and analysed as such. The same is true for participants administered an Ig infusion rescue medication during this time interval.

Participants are asked to record three grip strength score assessments at each day. The efficacy parameter will be derived from grip strength scores taken by a participant up to five days prior to the first IMP (for Baseline value) or visit date (for post Baseline visit value):

1. Maximum of grip strength assessments available at a particular day
2. Mean of maximum grip strength over most recent three non-missing days - up to a maximum of five days

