### 8.2.9 Use of rescue medication

The percentage of participants with concomitant medication identified as rescue medication [Yes/No] in the eCRF and time to first rescue medication administration will be summarized by treatment group and for all participants and listed by treatment group at each scheduled assessment during the Treatment and Observation Period.

If a participant receives rescue medication at multiple times, the relative day of the first occurrence is used to define the time to rescue medication.

The statistical methods applied to use of rescue medication and time to use of rescue medication will be the same as for CIDP relapse (iRODS), see Sections 8.2.1 and 8.2.1.1. The rule for handling missing data is described in Section 4.2.7.

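### After Visit 17, efficacy values are excluded according to relapse and not immunoglobulin exposure, so Observation Period results mix participants on and off immunoglobulin

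*SAP*

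**What the plan says.** The validity rule appears four times in the SAP, each time triggered by rescue medication alone:

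- Section 8, for all efficacy measures: "Any efficacy measurements are considered invalid, if the participant received rescue medication before the assessment". Such values leave the summary tables and the MMRM and stay only in listings. Same-day assessments remain valid.
- Section 3.5.4, for iRODS: "Measurements are considered invalid if the participant received rescue medication before the assessment of iRODS".
- Section 3.9, with the purpose: "To prevent bias in efficacy evaluation, an efficacy assessment is considered invalid, if that assessment follows the first intake of rescue medication".
- Section 4.2.1, for the premature end of treatment (PEOT) visit: "However, if a participant receives rescue medication prior to the PEOT visit, the assessment will be regarded invalid and only listed".

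SAP 8.2.9 identifies rescue as "concomitant medication identified as rescue medication [Yes/No] in the eCRF". Protocol 7.7.3 says what rescue is: "The subject will return to the SOC Ig treatment (eg, IVIg of 2g/kg) as rescue medication at the time of relapse".

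Protocol Table 8-1 sends two further groups back to Ig. For completers without relapse who choose SOC, the rescue column is marked not applicable and the entry reads "Subject returns to treatment with SOC (eg, IVIG or SCIG) during Observation Period". For participants withdrawn for reasons other than relapse, the rescue column says no and the entry reads "Subject returns to treatment with SOC (eg, IVIg or SCIG) during Observation Period". Both groups attend visits up to Visit 21.

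SAP 10.2 splits Observation Period TEAEs by whether SOC Ig had been received, using codes J06BA01 and J06BA02. The efficacy sections contain no such split.

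**The concern.** The rule is meant to keep the effect of restarted Ig out of the efficacy results. It does so only for people who restarted because they relapsed. Someone who restarts the same class of treatment by choice, or after stopping IMP for another reason, contributes every later value.

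Exclusion after Visit 17 therefore depends on relapse, which is itself an outcome, and not on exposure to Ig. The retained data are not a treatment-policy set, because Ig-treated relapsers are missing. They are not an off-Ig set either, because Ig-treated non-relapsers are present. At stake is whether the planned arm contrasts and summaries after Visit 17 have a definable meaning.

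**Working it through.** **1. The rule applied to each Table 8-1 path**

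| Path | On Ig after Visit 17/PEOT? | Labelled rescue? | Later efficacy values |
|---|---|---|---|
| Relapse in either period, Ig restarted | Yes | Yes | Dropped after the day of first rescue |
| Completer, no relapse, returns to SOC | Yes | No (not applicable) | Kept |
| Withdrawn for another reason, returns to SOC | Yes | No | Kept |
| Completer testing whether treatment is still needed | No, unless relapse | No | Kept |
| Completer entering the open-label extension at Visit 17 | Leaves the study | Not relevant | None |

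The first three paths share a treatment class, yet only the first is removed. The second and third are pooled with the fourth.

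**2. Which outputs this reaches**

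Collection visits are from Protocol 8.3.1 and 8.3.2; planned analyses are from SAP 8.2.1 to 8.2.8.

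| Measure | Visits after 17 | Arm contrast by model | Summary |
|---|---|---|---|
| Adjusted INCAT | 18, 19, 20, 21 | Yes (8.2.2) | Yes |
| Site grip strength | 19, 21 | Yes (8.2.3) | Yes |
| RT-MRC | 21 | Yes (8.2.6) | Yes |
| Patient-reported grip strength | 18 to 21 | MMRM planned; period not stated (8.2.4) | Yes |
| iRODS | 18 to 21 | Primary MMRM read as ending at Visit 17 | Yes (8.2.1) |
| CIDP PRO, fatigue, PGIS, PGIC | 21 | No | Yes, at item or category level |

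The model contrasts that certainly cover this period number 4 + 2 + 1 = 7. If the patient-reported grip strength model extends past Visit 17, 4 more are added, giving 11.

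**3. Week 13**

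- Completers finish Visit 17 before choosing SOC (Table 8-1).
- Withdrawn participants attend PEOT and then return to SOC in the Observation Period. SAP 4.3 maps visits after PEOT to the corresponding planned visits.
- Ig during the Treatment Period is handled as rescue. Protocol 7.7.2 refers prohibited IVIg and SCIg to section 7.7.3. In Protocol 6.4, the mandatory IMP discontinuation list reaches Ig only through the item on rescue or relapse. SAP 4.2.1 then voids a PEOT value that follows it.

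The primary analysis is therefore untouched. So are the relapse endpoints, which are defined up to Week 13 or during the Treatment Period.

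**4. Scale, on assumptions**

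The documents give neither the uptake of SOC Ig by arm nor the effect of Ig on these measures. In simple means, the shift in an arm contrast from retained on-Ig values is

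shift = (share on Ig in arm A − share on Ig in arm B) × d,

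where d is the Ig effect in SD units. I borrow 0.52 and 0.93 for d from SAP 2.4, purely as a scale. They are the plan's assumed sizes for rozanolixizumab versus placebo on the primary variable, not Ig effects. The plan's power figures for them reproduce: with 15 per group, a 1-sided 5% t-test and noncentrality d × √(15/2), power is 79.9% at 0.93 and 39.9% at 0.52, against the stated 80% and 40%.

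- Equal shares: 0.
- Shares 10 points apart: 0.10 × 0.52 = 0.052 to 0.10 × 0.93 = 0.093 SD.
- Shares 30 points apart: 0.30 × 0.52 = 0.156 to 0.30 × 0.93 = 0.279 SD.
- One extra on-Ig participant in an arm with 8 retained values: 0.52/8 = 0.065 to 0.93/8 = 0.116 SD. With 4 retained: 0.130 to 0.233 SD.

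The share differences and retained numbers are also assumed. Removing relapsers' later values adds a selection effect that this arithmetic does not capture.

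**The case against.** The strongest reply is that little depends on these outputs. SAP section 8 calls all efficacy analyses exploratory and presents no p-values. The Observation Period is non-randomised by design, since participants choose between the extension study, SOC and staying off treatment. The mixing thus comes from the protocol as well as the SAP rule. Listings keep every value, and medication listings carry dates, so the data can be traced. This stands, and it is why the point is minor.

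A second reply is that sites might flag SOC Ig as rescue, which would remove the asymmetry. The eCRF instructions are not available, so the realised effect is uncertain. But neither document asks for this, and Table 8-1 marks the two groups as not applicable and no.

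A third reply is that dropping every value after Ig has its own bias: it leaves mainly people who chose to stay off treatment and were not rescued. This also stands. It argues for showing results by Ig status and against relying on exclusion alone.

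A reader might also infer that the Week 13 result is exposed, through a PEOT value taken after Ig that was never flagged as rescue. The documents do not support this as a plan defect. Given the routing in Protocol 6.4, 7.7.2 and 7.7.3, it would be a recording error. It would also be prohibited medication, for which the per-protocol analysis can exclude specific data.

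**Conclusion.** The inconsistency is in the text and reaches planned outputs: at least seven model contrasts after Visit 17, plus the Observation Period summaries. As written, these can be read as neither on-Ig nor off-Ig results. The conclusion assumes that the eCRF flag is completed as Table 8-1 implies.

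Two stronger inferences are not supported. The bias has no known size or direction: the SD figures above show only how the shift scales with assumed inputs, and it is zero if the on-Ig shares are equal. Nor do the documents establish that the two groups receive an identical regimen; they establish the same class, IVIg or SCIg.

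Severity is minor: the primary analysis and the relapse endpoints are intact, and everything affected is exploratory.

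**What to change.** - Derive the date of the first Ig dose after first IMP, whatever its label, from J06BA01 and J06BA02 as SAP 10.2 already does.
- Present Observation Period efficacy by Ig status (on or off) using all observed values, including those after rescue.
- In SAP 8, with a note in 3.9, treat values after SOC Ig in the post-Visit 17 model contrasts in the same way as values after rescue Ig. Keep the same-day exception.
- State in 8.2.4 whether the patient-reported grip strength MMRM covers the Observation Period.
- State that arm contrasts after Visit 17 are descriptive only, because those who remain are a selected subset.
- Leave the FAS definition and the Week 13 analysis unchanged, except to state in 8.1.2 that Visit 17 is the last visit in the primary MMRM.

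The cost is some SAP wording, one derivation from codes already in use, one extra table, and fewer values in the Observation Period models. The table by Ig status keeps the excluded values visible.
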